### Switching date

The switching date will be defined using the following algorithm.

- For participants with non-missing Day 180 study treatment dose date, the switching date will be set to the Day 180 study treatment dose date.
- For participants with missing Day 180 study treatment dose date and non-missing Day 180 visit date, the switching date will be set to the Day 180 visit date.
- For participants with missing Day 180 study treatment dose date and missing Day 180 visit date, the switching date will be set to the study day 195 date.

If the resulting switching date locates after the study discontinuation date or the analysis cutoff date (if any), the switching date will be set to missing and the participant will be considered to have not switched until the study discontinuation or the analysis cutoff.

## Assessments and events allocation

In general, assessments and events will be allocated into the screening period, the core part and the extension part using the following rules.

- For non-randomized participants, all assessments / events will be considered as screening period assessments / events.
- For randomized participants, assessments / events with assessment date / event date prior to the randomization visit date will be considered as screening period assessments / events.
- For randomized participants with missing switching date, assessments / events with assessment date / event date on or after the randomization visit date will be considered as core part assessments / events.
- For randomized participants with non-missing switching date, assessments / events with assessment date / event date on or after the randomization visit date and on or prior to the switching date will be considered as core part assessments / events.
- For randomized participants with non-missing switching date, assessments / events with assessment date / event date after the switching date will be considered as extension part assessments / events.

## Study treatment allocation

In general, study treatments will be allocated using the following algorithm.

- Study treatments at the randomization visit and Day 90 will be considered as core part study treatments.
- Study treatments at Day 180 and Day 270 will be considered as extension part study treatments.

## Reflexive LDL-C

The LDL-C will be collected through the central laboratory, using the Friedewald formula and the ultracentrifugation method as appropriate. The calculated LDL-C (Friedewald formula) and the directly measured LDL-C (ultracentrifugation) will be loaded from the central laboratory.

The LDL-C endpoint will be derived using a reflexive LDL-C approach: either calculated LDL-C (based on the Friedewald formula) will be used, or if the calculated LDL-C is less than 70 mg/dL or triglycerides are greater than 400 mg/dL, or calculated LDL-C is missing, directly measured (using ultracentrifugation) LDL-C will be used if it is available.

## 2.2 Analysis sets

The following analysis sets will be used for statistical analyses:

The **Screened Set (SCR)** consists of all participants who signed the informed consent. The SCR includes only unique screened participants, i.e., in the case of re-screened participants only the chronologically last screening data is counted.

The **Randomized Analysis Set (RAS)** consists of all participants who received a randomization number, regardless of receiving trial medication.

The **Full Analysis Set (FAS)** consists of all randomized participants with the exception of those participants who have not been qualified for randomization and have not received study drug but have been inadvertently randomized into the study. Following the intent-to-treat (ITT) principle, participants will be analyzed according to the treatment they have been assigned to at randomization. Efficacy variables will be analyzed based on the FAS.

The **Safety Analysis Set (SAF)** includes all participants who received at least one dose of study drug. Participants will be analyzed according to the study treatment actually received. The SAF will be used for the analyses of safety variables.

[figure not shown]
The **Open-label Set (OLS)** includes all participants who entered the extension part and received at least one dose of study drug during extension part (at Day 180 or Day 270). OLS will be used to analyze the non-efficacy data in extension part, unless otherwise specified.

Participants without valid written informed consent will be excluded from all analysis sets. Further exclusions from the FAS are only justified in exceptional circumstances (e.g., site closed down for GCP reasons). The determination of which participants were excluded from the FAS is made in a blinded manner before the database lock for the Core Part.

Rules leading to exclusion from the analysis sets are given in [Appendix 5.5](#).

Note: The last part of the definition of the FAS is what is often referred to as mis-randomized participants i.e. participants for whom IRT calls were made by the site either prematurely or inappropriately prior to confirmation of the participant's final randomization eligibility and study medication was not administered to the participant. These participants would subsequently not continue to take part in the study or be followed-up. Mis-randomized participants will not be included in the FAS, but they will be included in the RAS.

## **2.3 Patient disposition, demographics and other baseline characteristics**

### **2.3.1 Patient disposition**

#### **Core part analyses**

The screening period completion status and the corresponding reason for non-completion will be collected for all participants with informed consent signed as the screening disposition and will be summarized using the number of screened participants, the number and the percentage of screened participants, who completed the screening period, and who discontinued during the screening period. In addition, the reason for discontinuation will also be summarized, using the number and the percentage of screened participants discontinued due to each reason. The SCR will be used for screening disposition.

The study completion status and the corresponding reason for non-completion will be collected for all randomized participants as the study disposition. The study disposition for core part will be summarized by treatment group separately using the number of randomized participants, the number and the percentage of participants who completed core part, and who discontinued from the study during core part. The reason for discontinuation during the core part will be summarized by treatment group separately, using the number and the percentage of participants discontinued due to each reason. The RAS will be used. Listing for study disposition will also be provided for core part.

The study treatment completion status and the corresponding reason for non-completion for core part will be summarized by treatment group, using SAF.

Duration on study is defined as: date of last known visit on study – date of study Day 1 + 1. For core part analyses, duration on study will be truncated at switching date. The duration on study will be summarized by treatment group for core part, using FAS.

Number of participants with protocol deviations will be tabulated by category (e.g., selection criteria not met, subject not withdrawn as per protocol, treatment deviation, prohibited

concomitant medication, other), deviation for core part, using RAS. Listing of participants with protocol deviation will be provided for core part.

The number of participants included in each analysis set will be tabulated by treatment group using SCR. Participants exclusion from analysis sets will be summarized for all participants with reasons for exclusion (i.e. including both protocol and non-protocol deviations) and corresponding listing will be provided.

### Final analyses

The study disposition for extension part will be summarized by treatment group separately using the number of randomized participants, the number of completed core part participants, the number and the percentage of participants who completed extension part, and who discontinued from the study during extension part. The reason for discontinuation during the extension part will be summarized by treatment group separately, using the number and the percentage of participants discontinued due to each reason. The RAS will be used. Listing for study disposition will also be provided for overall study.

The study treatment completion status and the corresponding reason for non-completion for extension part will be summarized by treatment group, using OLS.

Duration on study is defined as: date of last known visit on study – date of study Day 1 + 1. The duration on study will be summarized by treatment group for overall study using FAS.

Number of participants with protocol deviations will be tabulated by category, deviation for extension part and for overall study, using OLS and RAS, respectively. Listing of participants with protocol deviation will be provided for overall study.

The number of participants included in each analysis set will be tabulated by treatment group using SCR. Participants exclusion from analysis sets will be summarized for all participants with reasons for exclusion (i.e. including both protocol and non-protocol deviations) and corresponding listing will be provided.

#### 2.3.2 Demographics and other baseline characteristics

Summary statistics will be provided by treatment group for demographics and for other baseline characteristics, including age (years), age group (< 65 years,  $\geq$  65 years), sex, race, ethnicity, smoking history, alcohol history, protocol solicited medical history, ASCVD risk level, height, weight, body mass index (BMI), systolic blood pressure (SBP), diastolic blood pressure (DBP), pulse rate, eGFR, eGFR group (  $\geq$ 30 mL/min/1.73 m^2 to < 60 mL/min/1.73 m^2,  $\geq$  60 mL/min/1.73 m^2), LDL-C, PCSK9, TG, TC, HDL-C, non-HDL-C, ApoB, ApoA-1, Lp(a), where the BMI will be calculated as weight (kg) / [height (m)] from the height and the weight at screening. For variables only scheduled at screening, the scheduled assessment at screening will be summarized. For other variables, the baseline assessment will be summarized. Listings will also be provided.

The FAS will be used for the above summaries.

The above summaries for demographics and baseline characteristics will be conducted only in the core part analyses.

Medical histories will be collected using the medical history case report form (CRF) and coded using the Medical Dictionary for Regulatory Activities terminology (MedDRA). The collected medical histories will be summarized by treatment group, primary system organ class (SOC), and preferred term (PT), using the number and the percentage of participants with each medical history.

The FAS will be used for the above summaries.

The above summaries for medical histories will be conducted only in the core part analyses.

## **2.4 Treatments (study treatment, rescue medication, concomitant therapies, compliance)**

The SAF will be used for the analyses below, unless otherwise specified.

### **2.4.1 Study treatment / compliance**

The number and percentage of participants receiving study dose and the injection site location will be summarized by study visit and treatment group for both core part analyses and final analyses. For core part analyses, the summary tables including Day 1 and Day 90 visit and for overall study will be provided. For final analyses, the summary table will include Day 180, and Day 270 visit using OLS.

The number of doses received during the core part (at Day 1 and Day 90), duration of exposure, patient year of exposure will be summarized by treatment group for core part analyses. Such summary table of exposure to study treatment and listing for overall study will also be provided in core part analyses. The number of doses received during the whole study, duration of exposure for overall study and patient year of exposure will be summarized by treatment group for final analyses. Listings for overall study will also be provided in final analyses.

Duration of exposure for overall study will be calculated as: minimum of (Date of last dose of treatment – Date of first dose of treatment + 1 + 180, Date of last known visit – Date of first dose of treatment + 1). Duration of exposure to study treatment for overall study will be truncated at the analysis cutoff date for core part analyses.

The number of doses received during the extension part (at Day 180 and Day 270), duration of exposure in extension part and patient year of exposure will also be summarized by treatment group using OLS for final analyses. Duration of exposure for extension part will be calculated as: minimum of (Date of last dose of treatment in extension part – Date of treatment at Day 180 + 1 + 180, Date of last known visit in extension part – Date of treatment at Day 180 + 1). If the Day 180 treatment was not taken, then the date of Day 180 visit will be used.

Patient-year of exposure will be calculated as duration of exposure/365.25.

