9.2.3 Treatments

The SAF will be used for the analyses in this section.

Study treatment

The number and percentage of participants receiving study dose at each dosing visit will be summarized by treatment group. The number of doses received during the core part (excluding Day 180 dose) and during the extension part (including Day 180 dose) will also be summarized by treatment group.

Prior and concomitant therapies

Prior or concomitant medications will be summarized for the SAF in separate tabulations based on the coding dictionary used. Medications will be presented in alphabetical order, by Anatomical Therapeutic Chemical (ATC) class and preferred terms. Tables will show the overall number and percent of participants receiving at least one drug of a particular ATC class and at least one drug in a particular preferred term.

Prior medications and significant non-drug therapies will be summarized by treatment group. Concomitant medications and significant non-drug therapies prior to and after the start of the study treatment will be summarized by treatment group and by part.

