2. Participants randomized to Inclisiran Group will be treated with inclisiran sodium 300mg s.c. on Day 1 and Day 90 and Day 270, and with matching placebo s.c. on Day 180. Participants randomized to Control Group will be treated with matching placebo s.c. on Day 1 and Day 90, and with inclisiran sodium 300mg on Day 180 and Day 270.
3. The end of core part visit. The database lock for the core part is planned to occur after all randomized participants have completed the EOC visit (or have discontinued from the study before EOC). The primary endpoint analysis will be conducted after the database lock for the core part.
4. Participants who discontinue from study should be scheduled for an Early Exit visit if they agree. This Early Exit visit is suggested to be scheduled at least 30 days after last injection. If not possible, to set an Early Exit visit as soon as possible is also acceptable.

On Day 1 (Baseline), approximately 200 eligible participants who meet all inclusion and not meet any exclusion criteria will be randomized 1:1 to Inclisiran Group and Control Group. Study visits of core part will occur on Day 1 (baseline visit), Day 30, Day 90, Day 150, and Day 180. On Day 1 and Day 90 visits, inclisiran s.c. or placebo s.c. will be administered at the site by a healthcare professional. The primary endpoint will be assessed at Day 150. The EOC visit will be conducted on Day 180.

The extension part starts with a dose on Day 180 after all core part assessments are completed. In order to maintain the blind for the treatment group assignment, participants randomized to Control Group will receive inclisiran, while participants randomized to Inclisiran Group will receive placebo on Day 180. All participants will then receive inclisiran sodium 300 mg on Day 270, which will be the third dose of inclisiran for Inclisiran Group, and the second dose of inclisiran for Control Group. All injections will be administered at the site by a healthcare professional. The EOS visit (Day 360) will be the last visit of the study.

The randomization will not be stratified.

The core part analyses will be conducted when all randomized participants have completed the visit at Day 180 (or have discontinued from the study). The final analyses will be conducted when the trial ended. No interim analyses are planned.

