## 1.2 Study objectives, endpoints and estimands

**Table 1-1 Objectives and Endpoints**

Objective(s)	Endpoint(s)
Primary objective(s) 

To demonstrate the superiority of inclisiran as monotherapy, compared to placebo, on mean percentage change from baseline in LDL-C at Day 150, in Chinese adults with low or moderate ASCVD risk and elevated LDL-C who are not on any lipid lowering therapy.

	Endpoint(s) for primary objective(s) 

Percentage change in LDL-C from baseline at Day 150

Secondary objective(s) 

To demonstrate the efficacy of inclisiran as monotherapy, compared to placebo on absolute change from baseline in LDL-C at Day 150.

To demonstrate the efficacy of inclisiran as monotherapy, compared to placebo on percentage and absolute change from baseline in Proprotein Convertase Subtilisin/Kexin type 9 (PCSK9), total cholesterol (TC), high-density lipoprotein (HDL-C), non-high-density lipoprotein cholesterol (non-HDL-C), apolipoprotein B (ApoB), apolipoprotein A-1 (ApoA-1), lipoprotein (a) (Lp(a)) and triglycerides (TG) at Day 150.

To evaluate the effect of inclisiran as monotherapy on percentage and absolute change in LDL-C from baseline at Day 330.

To evaluate the safety and tolerability of inclisiran as monotherapy compared to placebo during core part.

To evaluate the safety and tolerability of inclisiran as monotherapy during extension part.

	Endpoint(s) for secondary objective(s) 

Absolute change in LDL-C from baseline at Day 150

Percentage change from baseline at Day 150 in PCSK9

Absolute change from baseline at Day 150 in PCSK9

Percentage change from baseline at Day 150 in TC, HDL-C, non-HDL-C, ApoB, ApoA-1, Lp(a) and TG

Absolute change from baseline at Day 150 in TC, HDL-C, non-HDL-C, ApoB, ApoA-1, Lp(a) and TG

Percentage change in LDL-C from baseline at Day 330 for inclisiran group

Absolute change in LDL-C from baseline at Day 330 for inclisiran group

Adverse Events (AEs), vital signs and safety laboratory values

Adverse Events (AEs), vital signs and safety laboratory values

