### **2.1.1 General definitions**

#### **Study treatment**

The term “study drug” or “study treatment” refers to the study drug (inclisiran sodium 300 mg s.c. or inclisiran-matching placebo) dispensed during the study.

For each participant and each dosing visit, the participant will be considered to have received the study treatment if the date of dose is non-missing and the answer to ‘was dose administered’ is yes.

For each participant, the first dose date and the last dose date of the study treatment are defined as the earliest date and the latest date on which the participant received the study treatment.

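### SAP 2.4.1 summarises doses and exposure of study treatment, placebo included, and plans no inclisiran-only summary for an extension objective that is about inclisiran

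*SAP*

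**What the plan says.** SAP 2.1.1 states that study drug or study treatment "refers to the study drug (inclisiran sodium 300 mg s.c. or inclisiran-matching placebo) dispensed during the study". Under SAP 1.1, "participants randomized to Inclisiran Group will receive placebo on Day 180", and the Day 270 injection is the one "which will be the third dose of inclisiran for Inclisiran Group". The Control Group receives inclisiran on both days.

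SAP 2.4.1 then summarises, by treatment group in the Open-label Set, "The number of doses received during the extension part (at Day 180 and Day 270"), together with exposure. The rule reads "Duration of exposure for extension part will be calculated as: minimum of (Date of last dose of treatment in extension part" minus the Day 180 treatment date, plus 1, plus 180. The other term of the minimum is the last known extension visit minus the Day 180 treatment date, plus 1. A missed injection does not move the start: "If the Day 180 treatment was not taken, then the date of Day 180 visit will be used". The whole-study formula has the same shape, counted from the first dose of study treatment.

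Protocol 9.2.3 prespecifies the same dose count: doses "during the extension part (including Day 180 dose) will also be summarized by treatment group". SAP 2.4.1 also plans a by-visit table of participants dosed, including Day 180 and Day 270. The objective these tables serve is, in SAP Table 1-1, "To evaluate the safety and tolerability of inclisiran as monotherapy during extension part".

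**The concern.** The extension objective concerns inclisiran, but its dose and patient-year tables measure injections of either product. The two groups will look equally dosed in the extension, although one receives half as many active injections as the other. In the whole-study table the Control Group will look as exposed as the Inclisiran Group, although its first two injections are placebo.

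This matters most for injection-site reactions. Protocol 2.3 names a higher incidence of injection-site events as the only inclisiran-related adverse drug reaction identified so far. SAP 2.7.1.1 tabulates these reactions by treatment group and study part, and neither label shows which product was injected. The date rules add a mismatch. SAP 2.1.1 assigns the Day 180 injection to the extension and sets the switching date to that injection's date. SAP 2.7.1 then places events starting on or before the switching date in the core part. A same-day reaction to a Control participant's first inclisiran injection is therefore a core-part event, while its dose is an extension dose.

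**Working it through.** The plan states no expected dose count or exposure figure, so there is none to reproduce. The formulas of SAP 2.4.1 are applied below to nominal visit days.

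**Inputs.** Inclisiran Group: inclisiran on Days 1, 90 and 270, placebo on Day 180. Control Group: placebo on Days 1 and 90, inclisiran on Days 180 and 270. Last visit Day 360 (SAP 1.1). The SAP's 180-day tail means a dose on day d counts through day d + 180. Protocol 4.3 describes six-monthly dosing after Day 90, which fits a Day 90 dose running to Day 270.

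**Dose counts, full compliance, per participant (Inclisiran v Control)**

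| | Study treatment | Inclisiran |
|---|---|---|
| Extension | 2 v 2 | 1 v 2 |
| Whole study | 4 v 4 | 3 v 2 |

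With 100 per group, the extension table shows 200 v 200 injections where inclisiran injections are 100 v 200. The whole-study table shows 400 v 400 where they are 300 v 200.

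**Exposure.** Inclisiran exposure here means days in the period that fall within the 180-day tail of an inclisiran dose.

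1. *Inclisiran Group, fully dosed, extension.* SAP: min(270 − 180 + 1 + 180, 360 − 180 + 1) = min(271, 181) = 181. Inclisiran: the Day 90 dose counts to Day 270 and the Day 270 dose past Day 360, so also 181. Removing the placebo from the record still gives 181.
2. *Control Group, fully dosed, whole study.* SAP: min(270 − 1 + 1 + 180, 360 − 1 + 1) = 360. From the first inclisiran dose: min(270 − 180 + 1 + 180, 360 − 180 + 1) = 181. The difference, 179 days, is placebo time.
3. *Inclisiran Group, Day 180 placebo is the last injection, followed to Day 360.* SAP extension: min(180 − 180 + 1 + 180, 181) = 181. Inclisiran: the Day 90 tail ends on Day 270, so 270 − 180 + 1 = 91. Whole study: 360 v 90 − 1 + 1 + 180 = 270. If the last visit is Day 330, the extension figures are 151 v 91. If it is Day 270 or earlier, they agree.
4. *Control Group, Day 180 visit without an injection, first inclisiran on Day 270.* SAP extension: min(271, 181) = 181. From Day 270: min(181, 360 − 270 + 1) = 91.

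**Effect of case 3 on the Inclisiran Group mean.** The documents give no rate, so a range is assumed. If a fraction f are such participants and the rest are fully dosed, the SAP mean is 181 and the inclisiran mean is 181(1 − f) + 91f.

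| f (assumed) | Inclisiran mean, days | SAP ÷ inclisiran |
|---|---|---|
| 2% | 179.2 | 1.01 |
| 5% | 176.5 | 1.03 |
| 10% | 172.0 | 1.05 |
| 20% | 163.0 | 1.11 |

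**The case against.** The strongest reply is that nothing is miscalculated. The tables describe study treatment, the SAP defines that term to include placebo, and the protocol prespecifies counting the Day 180 dose. Product is fixed by group and visit, so a reader can recover active doses from the planned by-visit table. Adverse events are reported as numbers and percentages of participants and no exposure-adjusted rate is planned, so patient-years are the denominator of no adverse-event result. All of this stands, and it makes the point one of labelling and completeness.

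Two stronger readings are tempting. A reader might infer that the SAP reports twice the true number of inclisiran doses. It does not, because the rows are not presented as inclisiran doses. A reader might also infer that Inclisiran Group extension exposure is overstated about twofold. For a fully dosed participant that figure arises only if the clock starts at Day 270 (181/91 = 1.99), which ignores cover from the Day 90 dose. A near-doubling needs the exceptions in cases 3 and 4.

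Nor can the effect on injection-site reaction percentages be sized. The documents give no per-injection risks, and same-day Day 180 reactions fall in the core part anyway.

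The reply leaves a gap. The by-visit table gives dose counts but not inclisiran exposure, and no planned table attributes injection-site reactions to the product injected.

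**Conclusion.** The point holds as a reporting gap. SAP 2.4.1 gives no inclisiran-only dose count or exposure, although the extension objective is the safety of inclisiran. With full compliance the study-treatment count hides a 1 v 2 split of inclisiran doses in the extension and 3 v 2 overall. It also credits each fully dosed Control participant with 360 days, against 181 from the first inclisiran dose.

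Extension exposure is right for Inclisiran Group participants dosed on Day 270. Overstatement (181 v 91 days at Day 360) is confined to cases 3 and 4. If 2–20% of the Inclisiran Group followed case 3, its mean would be about 1–11% too high as a measure of inclisiran exposure. These figures rest on nominal visit days, the SAP's own 180-day tail and the assumed rates. The efficacy analyses and the planned adverse-event percentages are unaffected.

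**What to change.** In SAP 2.4.1:

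- Label the existing rows 'study treatment (inclisiran or placebo)' and keep them.
- Add inclisiran-only dose counts for the extension and the whole study.
- Add inclisiran exposure computed from actual inclisiran dose dates, with the 180-day tail attached only to inclisiran doses and the Control Group's clock starting at the first inclisiran dose received.

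In SAP 2.7.1.1, add injection-site reactions by injection visit and product: Day 180 placebo, Day 180 inclisiran and Day 270 inclisiran. Include reactions that start on the Day 180 injection date, which the switching-date rule otherwise leaves in the core part.

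The cost is SAP wording and a few extra table rows. Protocol 6.2.3 already requires injections to be recorded in the eCRF and IRT and assigned kits in the IRT. The stated inclisiran exposure will be smaller than the study-treatment figure.
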